4. STUDY POPULATION

Subjects will have participated in Stage 2 of the randomized, double-blinded KARMET study ENT-01-030. All subjects who complete the treatment period in that study will be offered participation in this safety roll-over study.

Number of Subjects

Approximately 50 subjects will be included, and approximately 40 will complete all visits, assuming a 20% early termination rate.

5. SELECTION CRITERIA

Subjects will be screened according to the inclusion/exclusion criteria below.

Inclusion Criteria

1. All subjects who participated in the randomized study ENT-01-030 (KARMET Stage 2 Extension subjects) and who completed the dosing period.
2. Subjects aged 30-90 years at the time of screening for the ENT-01-030 study, both genders.
3. Subjects must provide informed consent and be willing and able to comply with study procedures.
4. Subjects must be able to read, understand, and accurately record data into the diary to guarantee full participation in the study.
5. Female subjects must have negative serum or urine pregnancy tests and must not be lactating. For females able to bear children, a hormonal (i.e., oral, implantable, or injectable) and single-barrier method, or a double-barrier method of birth control must be used throughout the study. A vasectomized partner will be allowed as one in conjunction with another single-barrier method.
6. Female subjects unable to bear children must have this documented in the CRF (i.e., tubal ligation, hysterectomy, or postmenopausal [defined as a minimum of one year since the last menstrual period]). Post-menopausal status will be confirmed by follicle stimulating hormone (FSH) in women less than 60 years of age.

Exclusion Criteria

1. Unable or unwilling to provide informed consent or to comply with study procedures.
2. Unable to withdraw proton pump inhibitors.
3. Unable or unwilling to withdraw from laxatives, opiates, clonazepam, or any medications which may cause constipation 2 weeks prior to the dose adjustment period and throughout the rest of the study.
4. Diagnosis of secondary constipation beyond that of Parkinson's disease.
5. A compromised gastrointestinal system which includes:
 - Structural, metabolic, or functional GI diseases or disorders.
 - Acute GI illness within 2 weeks of the screening visit.
 - History of major GI surgery within 30 days of the screening visit (a history of cholecystectomy, polypectomy, hernia repair or appendicectomy are not exclusionary as long as they were performed more than 30 days before the screening visit).
6. Neurological disorder other than Parkinson's disease that in the opinion of the investigator might interfere with the conduct of the study.

7. On treatment with intra-jejunal dopamine or carbidopa/levodopa (i.e. Duopa).
8. Subjects starting a new Parkinson's disease medication or modifying an existing medication within 2 weeks prior to enrollment.
9. Unable to maintain a stable diet regimen.
10. Subjects with a cognitive impairment that preclude them from understanding the informed consent.
11. Subjects placed under legal guardianship.
12. History of excessive alcohol use or substance abuse.
13. Any clinically significant abnormalities on screening laboratories or physical examination requiring further evaluation or treatment.
14. Females who are pregnant or breastfeeding.
15. Subject or caregiver unable to administer daily oral dosing of study drug.
16. Participation in a non-Enterin investigational drug trial within the month prior to dosing in the present study.
17. Any other reason, which in the opinion of the investigator would confound proper interpretation of the study.

6. DISCONTINUATION CRITERIA AND EARLY TERMINATION PROCEDURES

Subjects may withdraw voluntarily from participation in the study at any time and for any reason. Subjects may also be withdrawn on the basis of the Investigator's clinical judgment.

This study may be terminated at the discretion of the Enterin, Inc. or of any regulatory agency for reasons including safety and/or efficacy.

When a subject withdraws or is withdrawn before completing the study, the date and reason for withdrawal are to be documented. Subjects who withdraw or who are withdrawn prematurely are to attend an early discontinuation visit, at which time they will complete all Visit 4 assessments as outlined in [Appendix 2: Schedule of Events](#). The subject will be asked to return in 42 ± 3 days (6 weeks) to the site for Visit 5 as a safety follow-up visit.

In the event that a subject is withdrawn prematurely due to an adverse event or serious adverse event, the adverse event or serious adverse event will be followed until it resolves or stabilizes, or until it is judged by the investigator to be no longer clinically significant.

7. CONCOMITANT AND PROHIBITED MEDICATIONS AND THERAPIES

Categories of medications are listed below. Enterin will provide investigative sites with detailed listings of specific medications. All medications shall be reviewed and approved or disapproved by the investigator on a case-by-case basis.

Prohibited Medications to be discontinued at Screening (V1) and restarted during the wash-out period (V4):

- All oral laxatives, osmotic laxatives, pro-kinetic laxatives, stimulant laxatives, bulking agents, stool softeners, and suppositories, except for rescue medications used as directed in this protocol.
- Antacids
- Opiates
- Proton pump inhibitors
- Certain antipsychotics that worsen symptoms of Parkinson's disease.
- Certain antidepressants that worsen symptoms of Parkinson's disease.

Concomitant Medications permitted at stable doses

- Anticholinergics
- Antihistamines and anti-histaminergic agents
- Catechol-O-methyltransferase COMT inhibitors
- Certain antipsychotics
- Certain antidepressants, including tricyclic and quadricyclic antidepressants
- Dopamine agonists and amantadine (if on a stable dose for at least 2 weeks preceding the study).
- Certain dopamine reuptake inhibitors
- Dopamine metabolism inhibitors
- Dopaminergic compounds
- Selective serotonin reuptake inhibitors (SSRI)
- Serotonin and norepinephrine reuptake inhibitors (SNRI)

Permitted Therapies

- Deep brain stimulation, if present for more than 6 months and at stable stimulation parameters.

8. MATERIALS

8.1. Study Drug

All study medication will be supplied by Enterin, Inc. as 25 mg tablets packaged in white opaque high-density polyethylene (HDPE) bottles with child-resistant closures.

8.2. Packaging and Labeling

Study medication will be shipped to the investigational sites in packaging.

8.3. Storage, Dispensing and Reconciliation of Study Drug and Identity of Investigational Products

All study medication should be stored at 20°C to 25°C (68°F to 77°F) until dispensed, at which time subjects may keep it at room temperature. Storage on-site should be in a locked and secure location accessible only to site staff involved with this study. A temperature log must be kept to document temperature which should be recorded at least once each working day. If the temperature is not maintained, the sponsor should be contacted.

If a site becomes aware that study medication has not been properly handled, the sponsor must be contacted immediately. In such an event, study medication should not be dispensed to any subject until the sponsor provides further direction.

Neither the investigator nor any study personnel will distribute any study medication to any person not participating in this study. The study medication will be dispensed at the discretion and direction of the investigator in accordance with the conditions specified in this protocol. It is the investigator's responsibility to ensure that accurate records of study medication issuance and return are maintained.

The sponsor is responsible for the tracking and accountability of study medication dispensed to sites and will inform sites how to return or destroy study medication once it is no longer needed at the site.

Table 1: Identification of Investigational Product

Product Name	ENT-01
Dosage form	Tablet
Dosage level (mg)	25 mg
Route/dosage	Oral. Doses will require multiple tablets: 75 mg = 3 tablets 100 mg = 4 tablets 125 mg = 5 tablets 150 mg = 6 tablets 175 mg = 7 tablets 200 mg = 8 tablets 225 mg = 9 tablets 250 mg = 10 tablets
Dosing Instructions	Take 60 minutes before breakfast with 8 oz. water

9. WARNINGS AND PRECAUTIONS

Subjects will be advised to stay at home for 4-6 hours after taking the first dose of medication in case they need to evacuate urgently. Beyond the first dose, subjects themselves will be in a position to know if and when to leave the house.

10. STUDY PROCEDURES

10.1. Observations and Measurements

Subject informed consent must be obtained prior to conducting any study-related procedures. The Principal Investigator at each center will ensure that the subject is given full and adequate oral and written information about the nature, purpose, possible risk and benefit of the study. Subjects must also be notified that they are free to discontinue from the study at any time. The subject should be given the opportunity to ask questions and allowed time to consider the information provided.

All assessments and procedures will be completed according to [Appendix 2: Schedule of Events](#).

10.2. Instructions to Subjects

Prior to entry into the study, subjects and their spouse/companion will be instructed about the use of rescue medication.

10.3. CTCAE Definitions of Dose Limiting Adverse Events

Table 2: NCI CTCAE v. 4.03 Definitions for DLT Adverse Events

Adverse Event	Grade 1	Grade 2	Grade 3	Grade 4	Grade 5
Diarrhea (watery stool)	Increase of <4 stools a day over baseline	Increase of 4-6 stools a day over baseline	Increase of >7 stools a day; incontinence; hospitalization indicated	Life threatening complications: urgent intervention indicated	Death
Vomiting	1-2 episodes per 24 hours	3-5 episodes per 24 hours	6 or more episodes in 24 hours; tube feeding, TPN or hospitalization indicated	Life-threatening consequences: urgent intervention indicated	Death
Postural hypotension ³	Mild, transient lightheadedness or dizziness upon rising from lying or sitting position that does not interfere with ADL	Moderate lightheadedness, dizziness or fainting upon rising from lying or sitting position that limits instrumental ADL; Non-urgent medical intervention indicated	Severe lightheadedness, dizziness or fainting upon rising from lying or sitting position that limits self-care ADL; Medical intervention or hospitalization indicated	Life-threatening and urgent intervention indicated	Death

³Definition adapted from combining CTCAE definitions for Hypotension and Dizziness

10.4. Criteria for Dose Limiting Toxicity (DLT) Endpoints:

- Recurrent vomiting: 3-5 episodes of vomiting within 24 hours of taking study medication (Grade 2 adverse event)
- Recurrent diarrhea: >7 episodes of diarrhea within 24 hours of taking study medication (Grade 3 adverse event)
- Dizziness: Moderate lightheadedness or fainting upon rising from lying to sitting or standing and severe enough to require medical intervention within 24 hours of taking study medication (Grade 2 adverse event) or either a systolic blood pressure less than 80mmHg or diastolic blood pressure less than 40mm Hg.

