Study Product, Dose, Route, Regimen	ENT-01 will be administered in tablet form, once daily, on an empty stomach, first thing in the morning, with 8 oz of water. No food intake will be allowed for 60 minutes after taking medication. The tablets will be 25mg each. Subjects will begin dosing at the same dose level they were stratified to in the ENT-01-030 randomized study (i.e. , starting at either 3 tablets or 6 tablets,) and escalate up to a pro-kinetic dose or a maximum dose of 250mg.
Study Endpoints	
Safety Endpoints: Adverse events as evaluated with subject report, vital signs, chemical chemistry and electrocardiograms (EKG).
 
Tolerability Endpoints:
 
 • Recurrent vomiting defined as 3-5 episodes of vomiting within 24 hours. • Recurrent diarrhea defined as 7 episodes of diarrhea within 24 hours for 2 consecutive days. • Dizziness defined as lightheadedness or fainting on rising from lying to sitting or standing and severe enough to require non-urgent medical intervention within 24 hours. 
Primary Efficacy Endpoint:
 
 • Change from baseline in weekly CSBM rate during the 12 weeks of treatment over baseline. 
Secondary Efficacy Endpoints:
 
 • Change from baseline in the MDS-UPDRS score at the end of the 12-week fixed dose period. • Change from baseline in cognition as assessed by the MMSE at the 12-week fixed dose period.

	
 Change from baseline in psychosis as assessed by the SAPS-PD score at the 12-week fixed dose period.

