2. OBJECTIVES AND ENDPOINTS

2.1. Primary Safety Objective

To determine the safety and tolerability of orally administered ENT-01 for approximately 14 weeks in subjects with Parkinson's disease-related constipation.

Safety endpoints will include adverse events as evaluated with subject self-reporting, vital signs, clinical chemistry and hematology blood analyses, urinalysis, and electrocardiogram (EKG).

During the dosing period, it is anticipated that no more than 2 subjects out of 50 (4.0%) will have an adverse event of grade 4 or 5 that is at least possibly related to ENT-01. Should there be more than 2 subjects with an adverse event grade 4 or 5 that is at least possibly related to ENT-01 in the cohort of subjects, the study will be put on an immediate clinical hold. Safety Monitoring processes are identified in [Section 10.14](#).

In addition, individual safety stopping rules will include:

- Reaching dose-limiting tolerability (DLT) before a prokinetic effect
- Having a non-DLT gastrointestinal adverse event > grade 3 within 24 hours of taking study medication that is at least possibly attributable to ENT-01

Tolerability

Tolerability endpoints are referred to as the DLT and will include:

- Recurrent vomiting defined as 3-5 episodes of vomiting within 24 hours of taking study medication (i.e., a Grade 2 or higher AE, see [Table 2](#)).
- Recurrent diarrhea defined as 7 episodes of diarrhea within 24 hours of taking study medication on 2 consecutive days (i.e., a Grade 3 or higher AE, see [Table 2](#)).
- Dizziness defined as lightheadedness or fainting on rising from lying to sitting or standing that requires non-urgent medical intervention within 24 hours of taking study medication. (i.e., a Grade 2 or higher AE see [Table 2](#)).

It is anticipated that all subjects will exhibit a prokinetic effect at a dose lower than DLT and less than or equal to 250mg. Subjects reaching DLT before a prokinetic effect will be treated at the highest dose at which they did not experience a DLT.

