11.4. Tolerability Analyses

Tolerability will be measured by DLT endpoints as defined in [Section 10.4](#). The frequency of occurrence for each tolerability endpoint including recurrent vomiting, recurrent diarrhea, abdominal pain and dizziness will be summarized by treatment group and dose level for the Dose Adjustment period. Percentages will be based on the number of subjects in each dose level in the Safety Population.

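### The vomiting DLT in Section 10.4 is capped at 5 episodes, so the Section 11.4 tolerability table, read literally, leaves out the more severe cases

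*Combined protocol and SAP*

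**What the plan says.** Section 10.4, which sets the DLT criteria, gives for vomiting: "Recurrent vomiting: 3-5 episodes of vomiting within 24 hours of taking study medication (Grade 2 adverse event"). The synopsis, under Tolerability Endpoints, has "Recurrent vomiting defined as 3-5 episodes of vomiting within 24 hours" and no grade.

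Section 2.1 says that "Tolerability endpoints are referred to as the DLT", and for vomiting it reads "Recurrent vomiting defined as 3-5 episodes of vomiting within 24 hours of taking study medication (i.e., a Grade 2 or higher AE", with a pointer to Table 2. In Table 2 (Section 10.3), 3 to 5 episodes in 24 hours is Grade 2. Grade 3 is "6 or more episodes in 24 hours; tube feeding, TPN or hospitalization indicated".

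Section 11.4 fixes which definition is analyzed: "Tolerability will be measured by DLT endpoints as defined in" Section 10.4. The frequencies "will be summarized by treatment group and dose level for the Dose Adjustment period", and "Percentages will be based on the number of subjects in each dose level in the Safety Population".

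**The concern.** A dose-limiting criterion should be a threshold: once an event is bad enough to count, a worse one counts too. Section 10.4 and the synopsis instead give vomiting a ceiling as well as a floor, and the ceiling coincides with the upper edge of the Grade 2 cell in Table 2. Section 2.1 keeps the 3-5 count but calls it Grade 2 or higher, so it disagrees with Section 10.4 and with its own count.

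Tolerability is part of the primary safety objective, and Section 11.4 is the analysis that reports it by dose level. If the 3-5 range is programmed as written, a subject who vomits four times in a day is a DLT and a subject who vomits seven times is not. The error runs in the unsafe direction, because the DLT percentage at a dose level can only be too low.

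There is a second, conditional consequence. Reaching the DLT ends escalation (Section 3.2), sets the dose carried forward (Section 2.1) and is an individual stopping criterion (Section 10.15). A site that took Section 10.4 at its word could keep escalating after Grade 3 vomiting.

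**Working it through.** **The plan's only sample-size figure.** Section 11.7 gives 92% for seeing at least one AE with a 5% rate among 50 patients. 1 − 0.95^50 = 0.923, so it reproduces. This point does not depend on it.

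**Classification under each rule.** Grades are from Table 2.

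| Episodes in 24 h | Grade | Section 10.4 as written (3-5) | Section 2.1 gloss (Grade 2 or higher) |
|---|---|---|---|
| 0 | none | no | no |
| 1-2 | 1 | no | no |
| 3-5 | 2 | DLT | DLT |
| 6 or more | 3 | no | DLT |

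The rules differ only at 6 or more episodes.

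**Where those subjects would still appear.** Section 11.3 summarizes Grade 3 or higher AEs, so the events stay in the report. The breakdown it names is by organ class, preferred term and study period. The dose-level breakdown is in Section 11.4, where the omission falls.

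**Size per omitted subject.** Take a subject with 6 or more episodes and no separate 3-5 episode event at the same dose level. With n subjects at that level, the vomiting DLT percentage falls by 100/n points:

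- n = 50: 100/50 = 2.0
- n = 40: 100/40 = 2.5
- n = 20: 100/20 = 5.0
- n = 10: 100/10 = 10.0

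The protocol plans about 50 subjects and does not say how many will be at each level, so n = 10 to 50 is an assumption. n = 50 would need every subject to contribute to the same level, so it gives the smallest shift.

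**Exact 95% intervals (Clopper-Pearson).** With 0 events the upper limit is 1 − 0.025^(1/n). With 1 event the lower limit is 1 − 0.975^(1/n) and the upper limit is the 97.5th percentile of Beta(2, n − 1).

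| n | Shown if the subject is omitted | Shown if the subject is counted |
|---|---|---|
| 50 | 0% (0 to 7.1%) | 2.0% (0.05 to 10.6%) |
| 10 | 0% (0 to 30.8%) | 10.0% (0.25 to 44.5%) |

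**How likely is at least one such subject?** The documents give no vomiting rate by grade, and vomiting is not among the common AEs listed for the two earlier studies in Section 1. For assumed rates of 6 or more episodes, 1 − (1 − p)^50 gives 39.5% at p = 1%, 63.6% at 2% and 92.3% at 5%. These are illustrations, not estimates.

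**Dosing.** Section 3.2 gives its own episode count only for diarrhea, so for vomiting a site must look to Section 2.1 or 10.4. Section 3.2 cites neither, but it speaks of dose limiting tolerability, which is Section 2.1's term; the Grade 2 or higher gloss therefore probably governs. If a site used Section 10.4 instead, non-serious Grade 3 vomiting would not be a DLT. Section 10.15's rule for non-DLT gastrointestinal events would also miss it, because that rule requires a grade above 3.

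**The case against.** The strongest reply is that the intent is plain. Section 10.4 sits directly under Table 2 and labels each criterion with its entry grade; Section 2.1 renders each one as that grade or higher. Nobody would read Section 10.4 as excluding Grade 4 diarrhea, so what is missing is only the words *or more*. Dizziness has the same mismatch between the two sections. Nothing is lost from the report, since Section 11.3 provides listings and a Grade 3 or higher summary. The table at issue is descriptive and covers only the Dose Adjustment period. The detailed SAP is a separate document, so the actual derivation cannot be seen. Harm through dosing needs a site to treat three episodes as dose limiting and seven as not. Related SAEs stop the subject (Section 10.15), and the investigator may withdraw anyone (Section 6).

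Most of this is fair and limits the size of the point. It does not remove it. Section 11.4 sends the programmer to Section 10.4, where the count has a numeric ceiling and the grade is Grade 2 alone. The closed range is not a convention of that section either: the diarrhea line beside it is open upward. Dizziness differs because its requirement for medical intervention reads as a floor, so only alignment of wording is needed there. The dosing consequence stands only as a possibility, on the less likely reading.

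**Conclusion.** The point holds. The definition that Section 11.4 cites, followed as written, gives a wrong count: it includes 3 to 5 episodes and excludes the worse vomiting above that. Each subject affected lowers the dose-level vomiting DLT percentage by 100/n points, from 2.0 at n = 50 to 10.0 at n = 10, and a single subject can decide whether a level shows any vomiting DLT at all.

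This rests on a literal reading of Section 10.4, on assumed numbers per dose level, and on at least one subject having 6 or more episodes without a separate 3-5 episode event at that level. How often that would happen cannot be estimated from the documents. If the derivation already follows Section 2.1's gloss, nothing is omitted. No test, sample size or efficacy endpoint is touched. It is worth fixing because it is a contradiction in an operative safety criterion; the wording mismatch is certain, while the effect on dosing is only possible.

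**What to change.** In Section 10.4, Section 2.1 and the synopsis, define the vomiting DLT as 3 or more episodes of vomiting within 24 hours of taking study medication (Grade 2 or higher), and derive the Section 11.4 count from that. Only 6 or more episodes is reclassified; 0 to 5 is treated as before. At the same time, align the dizziness grade in Section 10.4 with Section 2.1 as an editorial change.

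The cost is a few words in three places. Whether any programmed derivation has to change is not known, because the detailed SAP is separate. The reported vomiting DLT rate may come out slightly higher.

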10.5. Pre-Existing Medical Conditions

All subjects enrolled in the study will have Parkinson's disease. Specific pre-existing medical conditions that will be excluded are listed in subject exclusion criteria.

10.6. Treatment Emergent Adverse events

A treatment-emergent adverse event (TEAE) is defined as any event not present prior to the initiation of the treatments or any event already present that worsens in either intensity or frequency following exposure to the treatments.

An adverse event is collected after signing the informed consent form and could be related or unrelated to the study drug. A TEAE is for after the subject actually takes the study drug.

Separate summaries for adverse events that occur during treatment (summary of treatment emergent adverse events) and adverse events occurring during the wash-out period will be provided.

